Ischemia/reperfusion injury and systemic inflammatory response syndrome are linked. After a period of ischemia, reperfusion stimulates the production of additional pro-inflammatory mediators, in particular, reactive oxygen free radicals and cytokines by parenchymal, endothelial, platelet, and inflammatory cells, contributing to elevated serum levels of inflammatory mediators. Cell death results from coagulation necrosis and inflammatory mediator-induced apoptosis. Endothelial cell injury results in impairment of the NO-cyclic guanosine monophosphate signaling cascade and endothelial-dependent vasodilatation (2). Alterations in NO generation appear to underpin the interrelationship of endothelial function and inflammation (3). NO might play several protective roles in reperfusion injury (4). NO is an important regulator of apoptosis, capable of both inducing and inhibiting apoptosis (5). NO has been shown to inhibit platelet adhesion and aggregation (6) and is able to block monocyte adherence and migration (7). Furthermore, NO is an inhibitor of leukocyte activation, preventing neutrophil-endothelial adhesion and the generation of oxygen free radicals (8).

The use of inhaled NO as a pulmonary vasodilator agent in neonates is well established. In addition to its potent vasodilatory effects in the pulmonary vasculature, inhaled NO has also been shown to have significant peripheral anti-inflammatory effects. The safety of perioperative administration of NO via the CPB circuit has been described in animals and human beings (9,10,11). Inhaled NO during adult cardiac surgery patients has been reported to reduce systemic inflammatory markers, attenuate endothelial dysfunction, and reduce ischemia/reperfusion injury (12,13,14). Administration of NO to adult patients undergoing cardiac surgery has been shown to blunt the release of markers of cardiac injury and decreases ventricular dysfunction during and immediately after CPB.

A more recent study in infants has also shown that the NO administration via the CPB circuit can reduce various markers of inflammation and reduce postoperative complications (15). To date, there have been no such studies relating NO administration via the CPB circuit and ischemia reperfusion injury in neonates undergoing surgical repair of congenital heart lesions.

4) Inclusion and Exclusion Criteria

Inclusion criteria:

- Neonates, age 0-30 days
- Full term, > 37 weeks gestation
- Birth weight ≥ 2.6 kg

Exclusion criteria:

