The data will be collected and saved on a password-protected Excel data sheet which will be stored on the password-protected computer of principal investigator.

12) Data Management

Sample Size Estimation

Sample size estimation was calculated using PASS 12 (15) based on the number of subjects needed to compare the difference in fluid balance as measured by the total amount of fluid administered in the first 24 and 48 hours for the two groups. Power analysis was run based on published data that showed a difference 130 mL between similar group assignments. (14) A sample size of 12 achieves 83% power to detect a mean difference of 75 mL with an estimated standard deviation of 60 mL and with a significance level (alpha) of 0.05 using a two sample t-test.

Data Management

Standard of care lab values and clinical indicators as identified in protocol Section 9 will be recorded in the electronic medical record (EMR) per routine hospital procedure. Lab values of markers being collected for research only will be received in a report directly from the labs. Investigators will extract study data from the EMR or lab results onto a source document for data collection and record into an electronic spreadsheet.

Statistical Analysis Plan

Data analysis will include measures of central tendency for all demographic and outcome variables. The primary endpoint of clinical indicators, including fluid balance, inotropic support, ventilator hours, and LOS will be compared between groups using a Repeated Measures ANOVA with post hoc comparisons, Student's t-test or chi-square as appropriate. A p-value less than, or equal to, 0.05 will be regarded statistically significant.

Secondary outcomes to be compared between groups include the biochemical markers. Analysis will be done using Student's t-test and a p-value less than, or equal to, 0.05 will be regarded statistically significant.

The other indicators, number of adverse events (as determined by methemoglobin) will also be described and reported as indicated in protocol Section 13. Differences in adverse event rates will be evaluated using descriptive and inferential statistics as appropriate.

Data Storage

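### The fluid outcome that sizes the trial is in mL and no covariate is planned; prespecifying birth weight as one covariate could gain precision at little cost

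*Combined protocol and SAP*

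**What the plan says.** The Sample Size Estimation paragraph of section 12 defines the powered outcome, fluid balance, as "the total amount of fluid administered in the first 24 and 48 hours for the two groups". It states that "A sample size of 12 achieves 83% power to detect a mean difference of 75 mL" "with an estimated standard deviation of 60 mL", at a "significance level (alpha) of 0.05 using a two sample t-test". The supporting literature figure is also a volume: "published data that showed a difference 130 mL between similar group assignments".

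The Statistical Analysis Plan in the same section says that the clinical indicators, fluid balance among them, "will be compared between groups using a Repeated Measures ANOVA with post hoc comparisons", or by Student's t-test or chi-square. It names no covariate and gives no unit for fluid balance.

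Body weight appears in section 4 as an entry criterion, "Birth weight ≥ 2.6 kg", with no upper limit. Section 10 calls the design a randomised block design but names no stratification factor. Weight is therefore handled neither in the allocation nor in the analysis.

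**The concern.** The volume of fluid a neonate receives plausibly depends in part on body size. If so, two things follow from leaving weight out. Weight-related variance stays in the error term, which lowers power. And with 12 per arm, randomisation can leave the arms noticeably different in mean weight, so that part of the observed mL difference reflects who was allocated where. In a trial this small, powered at 83% with no stated allowance for dropout, a baseline value already in hand is worth using if it explains even a modest share of the variance. Stating the choice in advance also removes the option of picking raw, per-kg or adjusted results once the data are seen.

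**Working it through.** **Inputs from the documents.** 12 per arm; difference 75 mL; SD 60 mL; alpha 0.05; two-sample t-test (section 12). Sidedness is not stated; two-sided is taken because it reproduces the stated power.

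**Inputs assumed.** r, the within-arm correlation of weight with total fluid, is not in the documents and is varied from 0 to 0.6. The 60 mL is taken as the total within-arm SD, including whatever part is due to weight. Weight is taken as roughly normal.

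**1. The plan's own figure.** Noncentrality = 75 / (60 × √(2/12)) = 75 / 24.5 = 3.06, with 22 degrees of freedom. Two-sided power from the noncentral t distribution is 83.3%, which matches the stated 83%.

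**2. Power with weight as covariate.** The residual SD is 60 × √(1 − r²), with 21 degrees of freedom. The standard error of the adjusted difference is residual SD × √(2/12 + d²/SSW), where d is the between-arm difference in mean weight and SSW is the within-arm sum of squares of weight. Power is averaged over the chance distribution of d and SSW.

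| Assumed r | Residual SD (mL) | Power for 75 mL |
|---|---|---|
| 0 | 60.0 | about 81% |
| 0.2 | 58.8 | about 83% |
| 0.3 | 57.2 | about 85% |
| 0.5 | 52.0 | about 91% |
| 0.6 | 48.0 | about 94% |

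Break-even with the unadjusted 83.3% lies just above r = 0.2. At r = 0 the loss is about 2 points: 83.3% against about 81%.

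**3. Chance imbalance in weight.** In units of the weight SD, the between-arm difference in means has SD √(2/12) = 0.408. The probability that it exceeds 0.5 in either direction is 2 × [1 − Φ(0.5/0.408)] = 2 × [1 − Φ(1.22)] = 0.22.

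**4. What an imbalance does to the mL difference.** One SD of weight corresponds to r × 60 mL of fluid, so an imbalance of 0.5 SD shifts the raw difference by 0.5 × r × 60 mL:
- r = 0.3: 9 mL, or 9/75 = 12% of the target.
- r = 0.5: 15 mL, or 15/75 = 20%.
- r = 0.6: 18 mL, or 18/75 = 24%.

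**The case against.** The strongest reply is that the planned test is already valid. Under randomisation the unadjusted t-test keeps its type I error, because its standard error covers chance differences in weight. This stands in full. A reader might infer from the imbalance figures that the planned comparison is biased; the documents do not support that.

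Second, the gain is unproven. A reader might infer that the plan certainly wastes precision, but the documents give neither a weight spread nor a correlation. Eligibility is narrow (term, birth weight floor, known genetic syndromes excluded, one operation), which tends to lower r. At r of 0.2 or less, adjustment gains nothing or loses slightly. This also stands; what remains is that the possible loss is small and the possible gain larger.

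Third, a much bigger shift can be made to appear by multiplying a weight imbalance by total intake per kg. With an assumed weight SD of 0.4 kg and 80 to 150 mL/kg, a 0.5 SD imbalance (0.2 kg) gives 16 to 30 mL. Against the plan's own 60 mL SD, those slopes imply r = 80 × 0.4/60 = 0.53 up to 150 × 0.4/60 = 1.0. At the top end weight would explain all the variation, which is not credible. The 9 to 18 mL range above is tied to the plan's SD and is the one to use.

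Fourth, the mL unit stands only in the sample-size paragraph. The analysis paragraph does not rule out per-kg reporting, so it would be too strong to say that it fixes a raw-mL comparison. It does not plan any alternative either.

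Last, the recorded criterion is birth weight, while section 30 puts surgery usually at 4 to 7 days of age. The data collection form (Attachment E) is not in the available text, so whether weight at surgery is recorded cannot be checked.

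**Conclusion.** The point holds as a matter of efficiency and interpretability, not validity. The powered outcome is a volume in mL, no covariate is planned, and birth weight is available for every subject. Adding it would move power from 83.3% to about 85 to 94% if r lies between 0.3 and 0.6, leave it about level near r = 0.2, and lower it to about 81% at r = 0. The arms have a 22% chance of differing by more than 0.5 SD in mean weight, and an imbalance of 0.5 SD would move the raw difference by 12 to 24% of the 75 mL target at r = 0.3 to 0.6. All of this rests on the assumed range for r and on 60 mL being the total within-arm SD. The change is worth making because the downside is small and bounded; the plan is not unsound without it.

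**What to change.** Before any unblinded review, add to the Statistical Analysis Plan that total fluid (mL) will be compared by ANCOVA on randomised arm with birth weight as the single covariate. Weight at surgery may be named instead if it is recorded for all subjects, but the plan should name one. Apply the model at each stated time point (24 h and 48 h), or enter weight as a covariate in the planned repeated-measures model, and say which. Report the adjusted mean difference in mL with a 95% confidence interval, and keep the unadjusted t-test as a sensitivity analysis. The timing matters because section 13 has the DSMB evaluate fluid balance at interim reviews, with access to unblinded data.

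With birth weight, the change needs no new data, no more subjects and no change to the 75 mL target. It costs a sentence or two of text and one degree of freedom, at most about 2 points of power if weight proves unrelated to fluid volume. It does not settle which of the several listed primary parameters, or which time point, carries the main conclusion; that needs its own statement.

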PROTOCOL TITLE: Efficacy of Nitric Oxide Administration in Attenuating Ischemia / Reperfusion Injury During Neonatal Cardiopulmonary Bypass Version3_6.3.16

Title: Efficacy of Nitric Oxide Administration in Attenuating Ischemia / Reperfusion Injury During Neonatal Cardiopulmonary Bypass

NCT: 02151877

Version 3_3Jun2016

Protocol Title

Efficacy of Nitric Oxide Administration in Attenuating Ischemia / Reperfusion Injury During Neonatal Cardiopulmonary Bypass

1) IRB Review History

N/A

2) Objectives

Hypothesis: The introduction of nitric oxide (NO) directly into the cardiopulmonary bypass circuit, during neonatal surgical repair of congenital heart lesions, will attenuate ischemia reperfusion injury that can complicate the surgical procedure and postoperative recovery.

Specific Objectives: During the Norwood procedure for hypoplastic left heart syndrome (HLHS) or its variants, there is around 20 to 30 minutes of ischemia to the myocardium between cardioplegia doses, and 20 to 30 minutes of interruption of flow to the lower body during reconstruction of the aortic arch. The proposed study will help to know if NO can decrease ischemia reperfusion injury to the myocardium, as well as to the lower body organs (liver, kidney, gastro-intestinal tract).

Specific Aims:

- 1) Evaluate whether NO delivered through the neonatal CPB circuit can decrease the clinical signs of ischemia/reperfusion injury and/or cardiac dysfunction as reflected by fluid balances, inotropic support, diuretic requirement, length of ventilator support, length of ICU stay, and length of hospital stay.
- 2) Evaluate whether NO delivered through the neonatal CPB circuit can decrease various biochemical markers of ischemia/reperfusion injury and oxidative damage [cardiac troponin I, interleukins (IL), tumor necrosis factor (TNF), N-terminal prohormone for brain natriuretic peptide (NT-proBNP), lactate dehydrogenase (LDH), plasma anti-oxidant levels, plasma malondialdehyde (MDA) levels].
- 3) Evaluate the safety of NO delivered through the neonatal CPB circuit as measured by adverse events during the course of the study.

3) Background

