- Preoperative sepsis
- Renal dysfunction, (preoperative creatinine greater than 1.0)
- Intracranial hemorrhage (preoperative intraventricular hemorrhage more or equal to grade 1)
- Known Chromosomal abnormalities and/or known genetic syndromes. (The Fluorescent in situ hybridization (FISH) test is routinely done on all neonates with cardiac disease. If the test results are not received before surgery, the subject will be withdrawn as indicated in protocol section 14.)
- Prior cardiac intervention, catheter-based or surgical
- RV wall and endocardial fibroelastosis (as determined by pre-operative echocardiography).

6) Study-Wide Number of Subjects

We will enroll a total of 24 subjects with 12 subjects in the treatment group and 12 subjects in the control group.

7) Study-Wide Recruitment Methods

The study will be performed at ACH-OL. The pediatric cardiac surgery division performs approximately 400 surgeries each year at this site. Twenty-four neonates with HLHS or its variants requiring surgical repair in the first few days of life will be randomized into 2 groups.

All newborns with diagnosis of HLHS or its variant, who undergo Norwood procedure and satisfy the inclusion criteria will be invited to participate in the study. Most of these patients are diagnosed prenatally by fetal echocardiography and are born at ACH-OL. Few patients with no prenatal diagnosis or who are born at an outside institution are transferred to ACH-OL for further management. Parents will

be informed about the study by our team of Pediatric Cardiac surgeons when they see the child for a clinical preoperative exam. This exam typically occurs after the child is born and the diagnosis is confirmed by echocardiography, and before the scheduled surgical procedure.

8) Study Timelines

The estimated duration needed to recruit the 24 subjects for the study is around 2 years. Each subject will be enrolled in the study from the time of surgery (Norwood procedure) until discharge. After all the subjects have been enrolled and the data has been collected, we anticipate that 2 to 3 months to finish analyzing the data and write the manuscript.

9) Study Endpoints

The primary study endpoints are to evaluate whether NO delivered through the neonatal CPB circuit can decrease the clinical signs of ischemia/reperfusion injury and/or cardiac dysfunction. Clinical parameters include:

- fluid balance
- diuretics requirement
- inotropic support
- duration of mechanical ventilation (hours)

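### Seven clinical outcomes are primary and judged at p ≤ 0.05 with no hierarchy, adjustment or success rule; if any one suffices, the family-wise error is about 12–30%, not 5%

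*Combined protocol and SAP*

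**What the plan says.** Three places define the primary endpoint, and they do not agree.

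- **Section 9 (Study Endpoints)** uses the plural: "The primary study endpoints are to evaluate whether NO delivered through the neonatal CPB circuit can decrease the clinical signs". Seven items follow: fluid balance, diuretics, inotropes, ventilation time, ICU stay, hospital stay and end-organ failure, the last measured by BUN, creatinine and liver function tests.
- **Section 12 (Statistical Analysis Plan)** says "The primary endpoint of clinical indicators, including fluid balance, inotropic support, ventilator hours, and LOS will be compared between groups". The method is repeated-measures ANOVA with post hoc comparisons, a t-test or chi-square, whichever is appropriate, and "A p-value less than, or equal to, 0.05 will be regarded statistically significant". Four indicators are named, but as examples. The Data Management paragraph of the same section refers to "clinical indicators as identified in protocol Section 9 will be recorded", so the term most naturally means the whole Section 9 list.
- **Section 13 (Data Analysis Plans and Interim Reports)** describes the primary endpoint, for the interim analyses, as fluid balance together with morbidity and mortality. Mortality is not on the Section 9 list.

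The sample size rests on one outcome, "fluid balance as measured by the total amount of fluid administered in the first 24 and 48 hours for the two groups", and the result is "A sample size of 12 achieves 83% power to detect a mean difference of 75 mL with an estimated standard deviation of 60 mL", at alpha 0.05 with a two-sample t-test. The text does not say whether the 75 mL and 60 mL belong to the 24-hour or the 48-hour total.

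**The concern.** Each test on its own keeps a 5% error rate. What is not controlled is the chance that at least one of the primary outcomes is significant when nitric oxide does nothing. With no ranking, adjustment or success rule, the plan does not prevent the trial from being called positive on whichever outcome crosses 0.05. The headline conclusion is therefore at stake.

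The stated power does not cover this situation. It describes the fluid test alone, at whichever window the 60 mL standard deviation belongs to, and says nothing about the other six outcomes.

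Timing adds to the problem. Section 13 has the primary endpoint evaluated at interim looks and each monitoring-board report passed to the principal investigator. It does not say whether those reports contain comparative efficacy results. If they do, an endpoint chosen late could be chosen with knowledge of them.

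**Working it through.** **Inputs from the documents.** 12 infants per arm (Section 6); seven primary outcomes (Section 9); threshold 0.05 per test, difference 75 mL, SD 60 mL (Section 12).

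**Assumptions.** One test per listed outcome, and any one significant result counts as success. The documents give no correlations, so a range is shown.

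**1. The plan's own figure.** Noncentral t with 12 + 12 − 2 = 22 degrees of freedom and noncentrality (75/60) × √(12/2) = 1.25 × 2.449 = 3.06. At two-sided 0.05 the power is 83.3%, which matches the stated 83%. At one-sided 0.05 it would be 90.7%, which does not. The sample size therefore assumes a single two-sided test at 0.05.

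**2. Seven independent tests.**
- Either direction: 1 − 0.95^7 = 30.2%.
- Benefit only, each test at 0.025: 1 − 0.975^7 = 16.2%. This count fits the aim in Section 2, to "Evaluate whether NO delivered through the neonatal CPB circuit can decrease the clinical signs of ischemia/reperfusion injury".
- Upper bounds under any dependence: 7 × 0.05 = 35% and 7 × 0.025 = 17.5%.

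**3. Seven correlated tests.** Simulated two-sample t-tests, 12 per arm, normal outcomes with equal pairwise correlation:

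| Correlation | Either direction (nominal 5%) | Benefit only (nominal 2.5%) |
|---|---|---|
| 0 (exact) | 30.2% | 16.2% |
| 0.3 | 27.4% | 13.9% |
| 0.5 | 23.4% | 11.7% |
| 0.7 | 18.3% | 9.2% |
| 0.9 | 11.7% | 5.9% |

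Equal correlation is a simplification. If only ventilation time, ICU stay and hospital stay correlate at 0.9 with one another, and all other pairs at 0, 0.3 or 0.5, the rates are 25.4%, 23.7% and 20.9% in either direction, and 13.4%, 11.9% and 10.5% for benefit only.

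**4. Other counts of tests, either direction.**
- Four (only the indicators named in the Section 12 sentence): 1 − 0.95^4 = 18.5% if independent, 9.4% at correlation 0.9.
- Ten (fluid at both windows adds one; BUN, creatinine and liver tests taken separately add two): 1 − 0.95^10 = 40.1% if independent, 13.2% at correlation 0.9, and at most 10 × 0.05 = 50%. Benefit only: 1 − 0.975^10 = 22.4% if independent, at most 25%.

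**5. Power if all seven stay primary.** Bonferroni gives 0.05/7 = 0.00714 per test. Power for 75 mL at SD 60 mL falls from 83.3% to 54.8%. For the cited difference ("Power analysis was run based on published data that showed a difference 130 mL between similar group assignments") it is 98.5% at SD 60 mL, and 93.0% or 83.1% at assumed SDs of 70 or 80 mL.

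**Limits.** The simulations use normal data and t-tests throughout, whereas Section 12 also allows repeated-measures ANOVA and chi-square. The biochemical markers, post hoc comparisons and interim looks are not counted.

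**The case against.** The strongest reply is that fluid is already the lead endpoint in all but name. It is the only outcome sized, it comes first in each list, and Section 12 uses the singular. If that were settled, with one window and no interim testing, its error rate would be 5%. The reading is reasonable, but no section states it, and Sections 9, 12 and 13 each place other outcomes beside fluid with equal standing. The window is not settled either.

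The error rates also rest on a success rule that the plan does not contain. That is true, and it is why they are conditional. But the plan does not exclude the rule, and that gap is the defect.

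Independence is implausible, since ventilation time and the two lengths of stay are linked. This objection stands against reading 30% as the expected rate. The scenario with those three outcomes linked gives 21–25%, and even a common correlation of 0.9 leaves more than twice the nominal level.

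The count of seven relies partly on a cross-reference in a sentence about recording data, not testing it. The four-test reading still gives 9–18%.

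Finally, a 24-infant, single-centre study might be regarded as exploratory. The protocol does not describe itself so. It states a directional hypothesis, a double-blind randomised design and a formal power calculation.

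**Conclusion.** The concern holds and must be fixed. The plan sets a 5% threshold for each outcome in a primary family of seven and gives no means of controlling error across the family. If any one result suffices and each outcome is tested once, the family-wise error in either direction lies between about 12% (correlation 0.9) and 30% (independence), and between about 6% and 16% for benefit only. The success rule and the correlations are assumptions. The absence of a hierarchy, adjustment or success rule, and the differing definitions in Sections 9, 12 and 13, are matters of text and need no assumption.

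**What to change.** Amend Sections 9, 12 and 13 so that all three name the same single primary endpoint.

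- **Primary.** Total fluid administered over one window, 24 or 48 hours, with its starting point stated. Use the window to which the 75 mL and 60 mL apply, and restate the power if they do not apply to it. Test by two-sample t-test at two-sided 0.05. State that the trial is positive only on this test.
- **Secondary.** The other fluid window, the other six Section 9 outcomes, and mortality and morbidity (with morbidity defined). Report deaths by arm as safety data as well. Specify in advance either Holm adjustment over a fixed list of tests or estimates with 95% confidence intervals and no claim of significance. Put the biochemical markers under the same rule.
- **Timing.** Date the choice and document that it was made without knowledge of unblinded interim results.

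**Cost.** An amendment, with no extra patients or data. The sponsor must trace which window the planning figures describe. A significant result on ventilation time or length of stay alone could no longer be called a positive primary result.

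**Alternative.** If the sponsor wants to keep seven primaries, fix the number of tests, adjust (for example Bonferroni at 0.05/7) and restate the power, which for 75 mL at SD 60 mL drops to 55%.
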